Changes in drinking behaviour including alcohol intake and cravings will be assessed weekly until Day 84 using the Alcohol TLFB and ACQ. Alcohol craving will also be assessed using a Craving VAS before and after dosing on Day 0.

Markers of alcohol use will be assessed at multiple timepoints, e.g., breath (Day 0 only), blood (Screening, Day – 3, 28 and 84) and urine (Screening and Days 1, 28, 56, and 84).

Alcohol withdrawal symptoms using CIWA-Ar will be assessed at Day 0.

Quality of life will be assessed by EQ-5D-5L at Screening and Days 28 and 84.

Patients will be invited to complete an optional semi-structured interview on Days 1 and 84 and to complete optional online psychological change questionnaire on Days -3, 1, 28, and 84.

Details of the methodology, interview structure and psychological changes measures can be found in the Psychological Change Study Manual.

Statistical methods:

[figure not shown]
This is an exploratory study and there are no null hypotheses to be tested.

Summary statistics will be presented for all function and safety parameters.

In general, descriptive statistics including number of observations, mean, standard deviation, median, minimum, and maximum will be presented for continuous parameters. Categorical parameters will be displayed using counts and percentages within each category.

Additional information is provided in the protocol. Full details of the statistical analysis will be provided in the statistical analysis plan (SAP).

Figure 1: Study Flow Diagram

NOTE: Patients will receive ongoing AUD relapse prevention psychotherapy throughout the study.

SCHEDULE OF EVENTS

TABLE 1: SCHEDULE OF EVENTS

Assessments/Procedures	Screening ¹	Psychedelic Preparation ² (In clinic or video call)			Dosing ³	Follow-up												
	Day -28 to -14	Day -12	Day -7	Day -3	Day 0	Day 1	Day 7	Day 14	Day 21	Day 28	Day 35	Day 42	Day 49	Day 56	Day 63	Day 72	Day 77	Day 84
		(± 5 days)		+2days		(± 2 days)			(± 4 days)									
General																		
Informed consent	X																	
Confirm eligibility	X				X													
Medical history	X																	
Demographics	X																	
Height/weight	X				X													X
Concomitant medication	X	X	X	X	X	X	X	X	X	X	X	X	X	X	X	X	X	X
Physical examination	X									X				X				X
Vital signs (HR, BP, and temperature) ⁴	X				X	X												X
ECG ⁷	X				X	X												X
Cardiac telemetry ²³					X													

Assessments/Procedures	Screening ¹	Psychedelic Preparation ² (In clinic or video call)			Dosing ³	Follow-up												
	Day -28 to -14	Day -12	Day -7	Day -3	Day 0	Day 1	Day 7	Day 14	Day 21	Day 28	Day 35	Day 42	Day 49	Day 56	Day 63	Day 72	Day 77	Day 84
		(± 5 days)		+2days		(± 2 days)			(± 4 days)									
Urine pregnancy (or serum FSH) test ⁵	X				X													
SETS ²⁰		X																
Diagnosis																		
Alcohol and drug use history ⁶	X																	
Biomarkers of Alcohol Use																		
Haematology including MCV and coagulation ¹⁶	X			X		X				X								X
Clinical biochemistry ¹⁶	X			X		X				X								X
Drug screening ¹⁶	X				X													
CDT ^{16, 24}	X			X						X								X
PK					X ¹⁸													
Urine EtG	X					X				X				X				X
Alcohol breath test					X													
Severity																		
Alcohol TLFB	X	X	X		X		X	X	X	X	X	X	X	X	X	X	X	X
SIP	X			X						X				X				X

Assessments/Procedures	Screening ¹	Psychedelic Preparation ² (In clinic or video call)			Dosing ³	Follow-up												
	Day -28 to -14	Day -12	Day -7	Day -3	Day 0	Day 1	Day 7	Day 14	Day 21	Day 28	Day 35	Day 42	Day 49	Day 56	Day 63	Day 72	Day 77	Day 84
		(± 5 days)		+2days		(± 2 days)			(± 4 days)									
Craving																		
ACQ					X	X	X			X				X				X
VAS craving					X ¹⁹													
Withdrawal																		
Withdrawal CIWA-Ar					X													
Psychiatric Disorders and Depression																		
MADRS (SIGMA)	X				X					X				X				X
MINI	X																	X ¹⁷
C-SSRS	X				X ²¹	X	X											X
CGIS	X					X				X				X				X
PGIC						X				X				X				X
Drug Experience																		
BPL-003 administration					X													
Nasal site reaction ⁸					X													
EDI					X ⁹													
MEQ30					X ⁹													
Readiness for discharge checklist ¹⁰					X													

Assessments/Procedures	Screening ¹	Psychedelic Preparation ² (In clinic or video call)			Dosing ³	Follow-up												
	Day -28 to -14	Day -12	Day -7	Day -3	Day 0	Day 1	Day 7	Day 14	Day 21	Day 28	Day 35	Day 42	Day 49	Day 56	Day 63	Day 72	Day 77	Day 84
		(± 5 days)		+2days		(± 2 days)			(± 4 days)									
Psychotherapy																		
Psychedelic preparation		X	X	X														
Psychedelic integration ¹¹						X	X	X										
Qualitative interview ¹³					X													
Semi-structured interview ¹²						X												X
Psychological change measures ¹²				X		X				X								X
Relapse prevention psychotherapy ¹⁴		X ¹⁵	X ¹⁵	X ¹⁵	X	X	X	X	X	X	X	X	X	X	X	X	X	X
Health Status and QoL																		
EQ-5D-5L	X									X								X
Treatment Model Feedback ²²											X							
Adverse Events																		
Adverse events	X	X	X	X	X	X	X	X	X	X	X	X	X	X	X	X	X	X
Reactivation Questionnaire							X			X								X

Abbreviations: ACQ = Alcohol Craving Questionnaire; AE = adverse event; ALT = alanine aminotransferase; AST = aspartate aminotransferase; AUD = alcohol use disorder; BP = blood pressure; CDT = carbohydrate deficient transferrin; CGIS = Clinical Global Impression of Severity; CIWA-Ar = Clinical Institute Withdrawal Assessment-Alcohol revised; C-SSRS = Columbia-Suicide Severity Rating Scale; ECG = electrocardiogram; EDI = Ego Dissolution Inventory; EQ-5D-5L = 5-level EuroQol-5 Dimension; EtG = ethylglucuronide; FSH = follicle-stimulating hormone; GGT = gamma-glutamyl transpeptidase; HR = heart rate; MADRS SIGMA = Montgomery–Asberg Depression Rating Scale, SIGMA version; MCV = mean corpuscular volume; MEQ30 = Mystical Experience Questionnaire; MINI = Mini-International Neuropsychiatric Interview; PGIC = Patient Global Impression of Change; PK = pharmacokinetics; QoL = quality of life;; SETS = Stanford Expectation of Treatment Scale; SIP = Short Inventory of Problems; TLFB = Timeline Follow-Back.

Notes:

1. Screening will occur from Day -28. The maximum time to complete Screening and Psychedelic Preparation will be 28 days.
2. The Psychedelic Preparation sessions may be completed in less than 12 days if the therapist has a good rapport with the patient, with a window of +/-5 days for Day -12 & Day -7, however they should not fall on the same day. The final preparation visit has a window of +2 days and should be Day -3 to Day -1 only. It is preferable that visits be face to face, but if necessary, visits can be completed remotely with the exception of Screening, Day -3, Day 0, Day 1, Day 28, Day 56, Day 84.
3. Unless otherwise indicated, ALL assessments, testing, and blood samples for haematology and clinical chemistry are to be performed PRIOR to dosing.
4. Vital signs (HR, BP, and temperature) at baseline will be measured in triplicate within 30 min (+/- 5mins) before dosing (Triplicate measurements should be obtained as closely as possible in succession, and no more than 2 min apart (temperature does not need to be repeated in triplicate). Predose BP must be within normal range pre dose on dosing day and if not repeated ~ 1 h later. If still not in range then it is considered a Screen fail. Vital signs also to be taken in triplicate within 30 min (+/- 5mins) before dosing Then single measurements at 10, 20, 30, 40 & 60 mins, and then every 30 min (+/- 5mins) until 4 h postdose; and when the patient is assessed as ready to be discharged on Day 0, if later than 4h postdose (as per the readiness for discharge questionnaire). Vital signs from 90 min post-dose onwards will form part of the readiness for discharge questionnaire. A note should be taken of any movement of the participant during Blood Pressure measurements. If systolic Blood pressure is > 160 mmHg then repeat the Blood Pressure measurement.
5. Pregnancy tests will only be done in women of childbearing potential. Urine pregnancy tests in women of childbearing potential will be done only at Screening and before dosing on Day 0. Serum FSH tests in postmenopausal women will be done at Screening only.
6. Including previous abstinence attempts.
7. ECG to be performed in triplicate at Screening (2 minutes apart), single at other visits.
8. A physician will examine the nostrils for any evidence of irritation or reaction after dosing with BPL-003.
9. EDI & MEQ30 To be completed after the qualitative interview, if done.
10. Readiness for discharge assessment to be completed every 30 minutes (+/- 5mins) starting 90 minutes after dosing before discharge from clinic up to 4 hours post dose. If the patient is not ready for discharge at 4 hours post dose then the questionnaire will be repeated again at the point Investigator believes patient may be ready for discharge.
11. The Psychedelic Integration Visit should be held in the clinic but may be done via video call at the discretion of the Investigator or for logistical reasons. The psychedelic integration on Days 1 and 7 should be started after all questionnaires/scales have been completed.
12. See Section 9.7.
13. Patients will be asked to take part in an optional qualitative interview. If they agree, the interview will commence on cessation of the psychedelic experience and before any postdose questionnaires are completed. The therapist will remain with the patient until the cessation of the psychedelic experience.
14. This can be either face to face or remote.
15. AUD relapse prevention psychotherapy (see [Appendix 4](#)) will begin during Psychedelic Preparation sessions.
16. Patients will fast (no food or drink, except water) for at least 8 hours before blood draws at the Screening visit

17. Only section I (AUD section) of the MINI to be completed at Day 84.
18. The PK blood sample will be taken three times after dosing at 5, 15 and 60 minutes post dose (+5 minutes for all timepoints) Details concerning the blood draw are provided in the Study Manual.
19. Craving VAS scale to be completed on admission and before discharge on dosing (Day 0). If greater at discharge than admission, then talk down and repeat scale and repeat until no higher than admission before discharging.
20. SETS will be administered prior to beginning the first psychedelic preparation session.
21. On Day 0 the C-SSRS will be done as part of discharge safety check at the end of Day 0.
22. Therapists may complete the Treatment Model feedback questions once from Day 15 to Day 42.
23. Cardiac Telemetry will be performed on Day 0 starting approximately 30 minutes before dosing up to 90 minutes post dose and any anomalies reported
24. CDT to be assessed in blood sample.

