3. STUDY ENDPOINTS

3.1. Primary Endpoints

Safety Endpoints

- Percentage of patients with treatment-emergent adverse events (TEAEs)
- Percentage of patients with clinically significant postdose abnormal laboratory tests
- Percentage of patients with clinically significant abnormal postdose vital sign measurements (HR, BP, and body temperature)
- Percentage of patients with postdose suicidal ideation as determined by the Columbia-Suicide Severity Rating Scale (C-SSRS)
- Change in C-SSRS score compared to Baseline at Days 7 and 84
- Readiness for discharge questionnaire
- Measure the frequency, emotional valence and functional impact of any re-activation events in the study through the Reactivation Questionnaire (ReAQ)

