4. Psychological therapies other than those planned per protocol that are initiated or terminated within 21 days of baseline and for the duration of the study
5. Has suicidal ideation with some intent to act within the 12 months before Screening, per the Investigator's clinical judgment or based on the Columbia-Suicide Rating Scale (C-SSRS), corresponding to a response of "Yes" on Item 4 (active suicidal ideation with some intent to act, without specific plan) or Item 5 (active suicidal ideation with specific plan and intent) for suicidal ideation on the C-SSRS, or a history of suicidal behaviour within the 12 months before Screening. Suicidal ideation with intent to act or suicidal behaviour as assessed on Day -3 should also be excluded
6. Suicide attempts and/or self-injurious behavior within 12 months before Screening.
7. Regular use of or dependence on other drugs other than caffeine or nicotine. Presence or history of SUD (not including AUD) as defined by the DSM-5. The Investigator will evaluate the patient's ability to abstain from using this substance during the study. The patient must have a negative recreational drug test on Day 0, before dosing
8. Any self-reported use of psychedelic compounds (phenethylamines, tryptamines, or dissociatives) in the past 6 months

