10.1.8. Columbia-Suicide Severity Rating Scale

Patient suicidal ideation will be assessed at the visits outlined in [Table 1](#) using the C-SSRS ([Posner, 2011](#)). The questionnaire will be administered by the Investigator or an appropriate delegate. The “baseline” questionnaire will be used at Screening, considering activity from the last 12 months, and the “since last visit” questionnaire will be used for subsequent visits.

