4.2 Study endpoint(s)

4.2.1 Primary endpoint(s)

Safety Endpoints:

- Percentage of patients with treatment-emergent adverse events (TEAEs)
- Percentage of patients with clinically significant postdose abnormal laboratory tests
- Percentage of patients with clinically significant abnormal postdose vital sign measurements (Heart rate (HR), Blood Pressure (BP), and body temperature)
- Percentage of patients with postdose suicidal ideation as determined by the Columbia-Suicide Severity Rating Scale (C-SSRS)
- Change in C-SSRS score compared to Baseline at Days 7 and 84
- Readiness for discharge questionnaire
- Measure the frequency, emotional valence and functional impact of any re-activation events in the study through the Reactivation Questionnaire (ReAQ)

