14.8.5 Columbia-Suicide Severity Rating Scale (C-SSRS)

Positive C-SSRS data defined as patients who answered “Yes” to any question will be listed.

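### Two C-SSRS primary endpoints have no planned summary or defined score, and the recall windows behind them blur predose and postdose ideation

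*Protocol*

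**What the plan says.** **Endpoints.** Protocol 3.1 lists "Percentage of patients with postdose suicidal ideation as determined by the Columbia-Suicide Severity Rating Scale (C-SSRS") among the primary endpoints. Protocol 3.1 and SAP 4.2.1 both add "Change in C-SSRS score compared to Baseline at Days 7 and 84".

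**Schedule.** The C-SSRS row of Protocol Table 1 is marked at Screening, Day 0, Day 1, Day 7 and Day 84, and is blank at Days -12, -7 and -3. Note 3 sets the default for the dosing day: "Unless otherwise indicated, ALL assessments, testing, and blood samples for haematology and clinical chemistry are to be performed PRIOR to dosing". Note 21 overrides it for this scale: "On Day 0 the C-SSRS will be done as part of discharge safety check at the end of Day 0".

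**Recall.** Under Protocol 10.1.8 the baseline version of the "questionnaire will be used at Screening, considering activity from the last 12 months"; every later visit uses the since-last-visit version.

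**Baseline.** Protocol 11.6 and SAP 12.2 take the latest value before dosing and fall back to Screening when nothing was recorded on Day -3 or predose on Day 0.

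**Eligibility.** Protocol 5.2.2.2, criterion 5 (criterion 27 in the synopsis) ends: "Suicidal ideation with intent to act or suicidal behaviour as assessed on Day -3 should also be excluded".

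**Analysis.** SAP 14.8.5 opens with "Positive C-SSRS data defined as patients who answered" yes to any question, and says that these data will be listed. In SAP 19.1 the only C-SSRS display is Listing 16.2.9.9.

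**The concern.** If the SAP is followed as written, the report will contain no percentage for the first C-SSRS endpoint and no change for the second. The protocol synopsis, under statistical methods, promises summary statistics for every safety parameter. SAP 4.2 marks some endpoints as reported separately, but not these two. SAP 17 declares one change only, to the flagging of laboratory values.

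If someone computes the two quantities later, the inputs mislead in two ways. The change would be measured against a reference form with a far longer recall than the postdose forms. The percentage would include a Day 0 form that cannot separate the hours after dosing from the days or weeks before it.

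Attribution matters beyond the final report. Data up to Day 1 feed any Safety Review Committee decision (Protocol 4.3), and the suicidality event of special interest is defined by C-SSRS items 4 and 5 or suicidal behaviour (Protocol 10.2.8).

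**Working it through.** The documents give no sample-size or error-rate figure for these endpoints, so there is nothing to reproduce. The check compares endpoints with displays and then does the recall-window arithmetic.

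**1. Displays for the seven primary endpoints (SAP 19.1)**

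- Treatment-emergent adverse events: Table 14.3.1.1
- Clinically significant laboratory results: Table 14.3.4.1
- Clinically significant vital signs: Table 14.3.6.4
- Readiness for discharge: Table 14.3.7.7
- Reactivation questionnaire: Table 14.3.7.8
- Postdose ideation on the C-SSRS: no table
- Change in C-SSRS: no table, and no score defined in SAP 14.8.5 or Appendix A

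**2. Predose and postdose forms.** Of the five scheduled C-SSRS assessments, one is before dosing (Screening) and four are after it (Days 0, 1, 7 and 84). The baseline rule can therefore only return the Screening form.

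**3. Windows in the change endpoint.** Screening looks back 365 days. The Day 7 form looks back to Day 1, which is 7 - 1 = 6 days at nominal timing. The ratio is 365 / 6 = 61 to 1. If a patient's tendency to ideation does not change, a positive answer is more likely over the longer window, so the comparison leans towards improvement.

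**4. The Day 84 form has two readings.**

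- Since the last visit (Day 77): 84 - 77 = 7 days. Days 7 to 77 are then covered by no C-SSRS, which is 70 / 84 = 83% of follow-up.
- Since the last C-SSRS (Day 7): 84 - 7 = 77 days, against 365 at Screening, a ratio of 4.7 to 1.

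**5. The Day 0 form.** Earliest discharge is 4 h after dosing. If the form reaches back d days before dosing, the postdose share of its window is 4 / (24d + 4).

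- Last visit read as the last C-SSRS, Screening at Day -28 to -14: 4 / 676 = 0.6% to 4 / 340 = 1.2%.
- Last visit read as the final preparation session, Day -3 to -1: 4 / 76 = 5.3% to 4 / 28 = 14.3%.

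On either reading most of the window is predose. The Day 1 and Day 7 forms follow a postdose assessment and do not share this problem.

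**6. Weight of one patient.** With 12 patients, 1 / 12 = 8.3 percentage points. The exact 95% interval is 0 to 26.5% for 0/12 and 0.2 to 38.5% for 1/12.

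**7. Day -3.** The exclusion criterion relies on an assessment that day. Table 1 marks neither the C-SSRS nor the MADRS (which has a suicidal-thoughts item) at Day -3.

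**The case against.** The strongest reply is that nothing essential is lost. The percentage needs no baseline, and four postdose assessments are scheduled. Positive answers are listed, SAP 19.1 adds complete listings of all data, and the Safety N is tabulated. With at most 12 patients and no hypothesis, anyone can count. Serious ideation or behaviour is also captured as an event of special interest and listed. A baseline is formally defined. Other checks exist around dosing: the MADRS is due on Day 0 before dosing and is reported item by item, and the discharge questionnaire asks about acute suicidal ideation from 90 minutes.

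Much of this stands. A reader might infer that the two endpoints cannot be obtained. The documents do not support that: the percentage can be counted from the listings, and the change has a nominal Screening baseline. A reader might also infer that the criterion requires a C-SSRS on Day -3. Its Day -3 sentence names no instrument, and the same criterion accepts clinical judgement as well as the scale.

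Three things remain. A listing is not a prespecified percentage or change, and small numbers do not explain why five primary endpoints have tables and these two do not. A nominal baseline with a different recall period is not a comparable one. The MADRS item and the discharge check do not replace endpoints defined by the C-SSRS.

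**Conclusion.** The point holds as an undeclared analysis gap with a measurement problem behind it. Two of the seven primary endpoints have no planned summary, and one of them uses a score that is nowhere defined. The change endpoint compares 12 months with about 6 days at Day 7. The Day 0 form mixes predose and postdose time, and one misattributed patient in 12 is worth 8.3 points. The Day -3 wording and Table 1 do not agree.

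The direction of the bias rests on one assumption: that the patient's underlying tendency to ideation is unchanged. Its size cannot be taken from the documents. A reader might infer an artefact of 60 to 90 percentage points at Day 7. That needs every patient to have episodes at a constant rate between one a year (63.2% against 1.6% for any positive answer) and one per 90 days (98.3% against 6.4%). No document gives such a rate. Ideation at items 4 or 5 and suicidal behaviour in the previous 12 months are excluded, so the artefact mainly concerns milder ideation. If only 10% of patients had the one-a-year rate, also an assumption, the gap would be 0.1 x (63.2 - 1.6) = 6.2 points, less than one patient in 12. The size is therefore left open.

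**What to change.** 1. **SAP 14.8.5 and 19.1:** add a table of n/N (%) of Safety-population patients with any postdose ideation and with any suicidal behaviour, overall and by visit. An exact interval is optional at this size.
2. **Change endpoint:** replace the undefined change in score with a shift or worst-category table. Show the 12-month Screening form as history. Do not interpret a difference from it as change unless a predose since-last-visit form exists.
3. **Recall windows:** state that the Day 0 form covers the time since dosing and the Day 84 form the time since the last C-SSRS. Where data are already collected, flag Day 0 positives whose onset may be predose.
4. **Day -3:** reconcile Table 1 with the exclusion criterion. If the outcome is a C-SSRS on that day, use it as the analysis reference.
5. **SAP 17:** record the departure from the protocol's stated endpoint summaries.

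Items 1, 2 and 5 cost two small tables and a few sentences. They need only existing data and can be done before database lock, even if dosing is over. The prospective parts of items 3 and 4 cost a footnote and, depending on how item 4 is resolved, one short questionnaire at an existing visit. They help only patients not yet dosed.

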1. INTRODUCTION

1.1. Alcohol Use Disorder

The Diagnostic and Statistical Manual of Mental Disorders, Fifth Edition (DSM-5) integrates 2 DSM-IV disorders—alcohol abuse and alcohol dependence—into a single disorder called alcohol use disorder (AUD) with mild, moderate, and severe subclassifications. The key feature of AUD is the impaired ability to stop or control alcohol use despite adverse social, occupational, or health consequences. Severity is based on the number of criteria a person meets based on their symptoms—mild (2 to 3 criteria), moderate (4 to 5 criteria), or severe (6 or more criteria). DSM-5 lists the following criteria ([American Psychiatric Association, 2013](#)):

In the past year, have you

- Had times when you ended up drinking more, or longer, than you intended?
- More than once wanted to cut down or stop drinking, or tried to, but couldn't?
- Spent a lot of time drinking? Or being sick or getting over other aftereffects?
- Wanted a drink so badly you couldn't think of anything else?
- Found that drinking—or being sick from drinking—often interfered with taking care of your home or family? Or caused job troubles? Or school problems?
- Continued to drink even though it was causing trouble with your family or friends?
- Given up or cut back on activities that were important or interesting to you, or gave you pleasure, in order to drink?
- More than once gotten into situations while or after drinking that increased your chances of getting hurt (such as driving, swimming, using machinery, walking in a dangerous area, or having unprotected sex)?
- Continued to drink even though it was making you feel depressed or anxious or adding to another health problem? Or after having had a memory blackout?
- Had to drink much more than you once did to get the effect you want? Or found that your usual number of drinks had much less effect than before?
- Found that when the effects of alcohol were wearing off, you had withdrawal symptoms, such as trouble sleeping, shakiness, restlessness, nausea, sweating, a racing heart, or a seizure? Or sensed things that were not there?

According to the World Health Organization (WHO), in 2018 there were 380 million people with AUD worldwide (5.1% of the population over 15 years of age, representing 7.1% and 2.2% of the global burden of disease for males and females, respectively). Alcohol is the leading risk factor for premature mortality and disability among those aged 15 to 49 years, accounting for 10% of all deaths in this age group. Disadvantaged and especially vulnerable populations have higher rates of alcohol-related death and hospitalization. Globally, alcohol is directly responsible for about 3 million deaths per year (about 5.3% of all deaths) in addition to disabilities and poor health ([WHO, 2018](#)). Harmful use of alcohol causes a range of mental and behavioural disorders and is associated with the incidence of infectious diseases such as tuberculosis as well as the

course of human immunodeficiency virus/acquired immunodeficiency syndrome (HIV/AIDS), other noncommunicable conditions, and injuries. Beyond individual problems, alcohol abuse leads to significant social and economic losses to society at large. Both acute and chronic heavy drinking can contribute to a wide range of social problems, including domestic violence and marital breakdown, child abuse and neglect, absenteeism, and job loss (Meloni, 2004). In fact, according to a multicriteria decision analysis of drug harm in the United Kingdom (UK), alcohol was the most harmful drug (overall harm score 72), with heroin (55) and crack cocaine (54) in second and third places, driven by the overwhelmingly high harm to other people resulting from an individual's alcohol misuse (Nutt, 2010).

According to The National Institute for Health and Care Excellence (NICE) guidelines, treatment for AUD includes brief interventions to facilitate more healthy behaviours; specialised treatment like motivational enhancement therapy to address ambivalence about changing their drinking behaviour or dealing with their problems; detoxification to address withdrawal symptoms; cognitive-behavioural therapies to avoid relapses; and several drugs to diminish cravings or discourage relapses (National Institute for Health and Care Excellence, 2019). For people with severe alcohol dependence and/or significant physical or psychiatric comorbidity, this may require medication-assisted alcohol withdrawal in an inpatient or residential setting (Specialist Clinical Addiction Network, 2006). Current United States (US) Food and Drug Administration (FDA)-approved pharmacological treatments include acamprosate, naltrexone, and disulfiram. Scientific evidence demonstrates the benefits of combining approved drugs for treating AUD with evidence-based behavioural therapy, and the outcomes are generally better when medication and therapy are combined (Mason, 2021). Other emerging and off-label pharmacotherapies include nalmefene, which was approved in Europe and Australia for the purpose of controlling drinking, baclofen, topiramate, and gabapentin (Morley, 2021).

Peer-support group counselling is an approach used to facilitate relapse prevention. Alcoholics Anonymous is one of the earliest organizations formed to provide peer support and it is still the largest; other organisations exist for those who do not agree with the Alcoholics Anonymous philosophy (Kelly, 2020). Yet, despite all the harms and a variety of treatment options, only 19.8% of individuals with lifetime prevalence of AUD have sought treatment (Grant, 2015). Most studies examining the outcomes of people attending alcohol treatment find that 70% to 80% will relapse in the year following treatment, with the highest rate of relapse taking place in the first 3 months after completing treatment (Schuckit, 2009). Poor treatment response is typically associated with greater baseline alcohol use severity indicators (Davis, 2018a; Saitz, 2010), suggesting an unmet intervention need in heavy users.

